8.1.1. Six-point Ordinal Clinical Recovery Scale

The 6-point ordinal clinical recovery scale provides 6 mutually exclusive conditions ordered from best to worst, and the score reflects the participant's worst situation on the day assessed. The sponsor will assign the ordinal scale category based on the assessment of the participant's clinical status by the investigator. The ordinal clinical recovery scale categories are defined below.

Ordinal Clinical Recovery Scale (and Definitions)^a

1. Not hospitalized^b

Any of the following:

- Discharged from the hospital the day of assessment
- Hospitalized at the day of assessment but ready for discharge on the day of assessment, as judged by the investigator (eg, if still hospitalized in case of lack of bed availability in a skilled nursing facility, lack of social support at home).

2. Hospitalization, not requiring supplemental oxygen

^a Alternate care settings delivering care which would normally be delivered in a hospital setting will be categorized as hospitalized.

If a participant was discharged from the hospital “Against Medical Advice” on the day prior to the day of assessment, the participant will be categorized per the definitions above in the category the participant was in at the moment of discharge “Against Medical Advice”. The hospital recovery scale category will be considered missing on subsequent days.

If a participant declines medically-indicated mechanical ventilation, the participant will be categorized according to the care they would otherwise have received on that day.

^b A distinction will be made between participants discharged and in need of (score 1.2) or not in need of (score 1.1) oxygen supplementation as indicated by the investigator on the discharge questionnaire. This distinction will not be made when calculating improvements on the CRS, for which score 1 will be used in both cases.

3. Hospitalized, requiring low flow supplemental oxygen

- Hospitalized on the day of assessment (including readmittance), and supplemental oxygen is required by the participant.

Requiring supplemental oxygen is defined by:

- Receiving supplemental oxygen for instance through a face mask or nasal cannula, at a $\text{FiO}_2 < 50\%$,^a and not being able to sustain a blood oxygen saturation of $>93\%$ when breathing room air.

OR

- Not receiving supplemental oxygen and having a blood oxygen saturation of $\leq 93\%$ sustained for 5 minutes.

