5.2 Primary Efficacy Endpoint(s)

5.2.1 Definitions

Six-point ordinal clinical recovery scale

The 6-point ordinal clinical recovery scale (CRS) provides 6 mutually exclusive conditions ordered from best to worst, and the score reflects the participant's worst situation on the day of the assessment:

1. Not hospitalized
2. Hospitalized, not requiring supplemental oxygen
3. Hospitalized, requiring low flow supplemental oxygen
4. Hospitalized, on non-invasive ventilation, nonrebreather mask or high flow oxygen device
5. Hospitalized, on IMV or ECMO
6. Death

The CRS can be derived from baseline up to and including day 28. The CRS will be missing after trial discontinuation if the participant discontinued the trial for other reason than death. Participants who die before day 28 (before or after discharge from hospital) will be considered to continue the trial up to and including day 28.

The CRS categories are defined below. For ease of categorization, the categories are defined from worst to best. A participant will be evaluated in the same ordering of the categories as below. Once a participant fulfils the criteria for a category, the category is assigned to the participant and the evaluation stops.

6. Death
 - o Participant died at any time on the day of assessment or earlier (all-cause mortality).
5. Hospitalized, on IMV or ECMO

- o IMV or ECMO is used at any time on the day of assessment, OR
- o From a Medical Perspective, the participant should have been on IMV on the day of the assessment

4. Hospitalized, on non-invasive ventilation, nonrebreather mask, or high flow oxygen device
 - o The participant is on supplemental oxygen and the worst FiO₂ is $\geq 50\%$.
3. Hospitalized, requiring low flow supplemental oxygen
 - o On supplemental oxygen with worst FiO₂ $< 50\%$ and the participant was not able to sustain a blood oxygen saturation of $> 93\%$ when breathing room air, OR
 - o Not on supplemental oxygen and the minimum of all available SpO₂ values during the day is $\leq 93\%$
2. Hospitalization, not requiring supplemental oxygen
 - o Hospitalized according to the status described below
1. Not hospitalized, including subjects on low level of oxygen

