 - o A distinction will be made between subjects discharged and in need of (score 1.2) or not in need of (score 1.1) oxygen supplementation as indicated by the investigator on the discharge questionnaire. This distinction will not be made when calculating improvements on the CRS, for which score 1 will be used in both cases.

Hospitalization status

The hospitalization status considered for the definition of the CSR will be defined according to the rules described below. The hospitalization status will be evaluated in the same ordering of rules. Once a participant fulfils the criteria, the hospitalization status is defined and the evaluation stops.

1. If a participant is discharged to the alternate care settings ‘different hospital’, ‘acute care facility’, ‘subacute care facility’ or ‘hospice/palliative discharge’, the participant will be considered hospitalized until day 28 or trial discontinuation, whichever comes first. The participant will be categorized in the category the participant was in at time of discharge until trial discontinuation.
2. If a participant is discharged ‘against medical advice’, the participant will be considered hospitalized on the day of discharge and on the day after discharge, unless the participant discontinued the trial. The participant will be categorized in the category the participant was in at time of discharge. The CRS will be considered missing from 2 days after discharge onwards.
3. If a participant is hospitalized although ‘ready for discharge’ according to the investigator, the participant will be considered hospitalized up to and including the first day on which the participant was considered ready for discharge. The participant will be considered “Not hospitalized” from the day after until day 28 or trial discontinuation, whichever comes first (unless the status changes back to “not ready for discharge”).
4. If a participant is discharged although ‘not ready for discharge’ according to the investigator, the participant will be considered hospitalized up to and including 1 day

after the day of discharge, unless the participant discontinued the trial. The participant will be categorized in the category the participant was in at time of discharge. The participant will be considered non hospitalized from 2 days after the day of discharge onwards until day 28 or trial discontinuation, whichever comes first.

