5. If a participant is discharged from the hospital, the day of discharge will be considered as “hospitalized”. The participant will be categorized in the category the participant was in at time of discharge. After this day, the participant will be considered “Not hospitalized” until day 28 or trial discontinuation, whichever comes first.

Baseline

The 6-point ordinal CRS at the time of randomization request will be used as the baseline. If the baseline assessment of the CRS is missing, the first available assessment within 12 hours after randomization will be used. If the latter is also missing, the last available assessment prior to baseline will be used.

Sustained Clinical Improvement

Clinical Improvement is obtained if the score on the CRS improved with at least 2 categories with respect to the baseline score.

Sustained clinical improvement is defined as a clinical improvement without documented loss of this clinical improvement up to and including day 28 or until trial discontinuation, whichever comes first.

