3. If a subject is hospitalized, but is ‘ready for discharge’ according to the investigator, the subject will be considered hospitalized up to and including the first day on which the subject was considered ready for discharge. The subject will be considered “Not hospitalized” from the day after until day 28/trial discharge (unless the status changes back to “not ready for discharge”).
4. If a subject is discharged, but is ‘not ready for discharge’ according to the investigator, the subject will be considered hospitalized up and including 1 day after the day of discharge or until trial discontinuation. The subject will be categorized in the category the subject was in at the moment of discharge. The subject will be considered non hospitalized from 2 days after the day of discharge onwards until day 28/trial discontinuation.
5. If a subject is discharged from the hospital, the day of discharge will be considered as “hospitalized”. The subject will be categorized in the category the subject was in at the moment of discharge. After this day, the subject will be considered “Not hospitalized” until day 28/trial discontinuation.

CRS Derivation

The Ordinal Clinical Recovery Scale can be derived from Baseline up to and including Day 28, or until trial discontinuation. Participant who died before day 28 (before or after hospital discharge, but before trial discontinuation) will be considered to continue the trial up to and including day 28.

For the derivation, we will start with the highest score.

If the subject didn't fall into this category, we will check for the next highest score.

- **Score 6:** Based on the status of the participant on the day of the assessment (based on the date of death).

Based on Type of Oxygen Supplementation page:

- **Score 5:** At least one of the following scores is ticked:
 - IMV
 - Extra Corporeal Membrane Oxygenation
 - The question “Is the subject on Mechanical Ventilation” is answered “No”, and the question “From a Medical Perspective, should the patient be on IMV?” is answered “Yes”. (on Subject Status Form)*
- * To comply with the note: “*If a participant declines medically-indicated mechanical ventilation, the participant will be categorized according to the care they would otherwise have received on that day*”
- **Score 4:**
 - Subject is on supplemental oxygen and the FiO2 is $\geq 50\%$.
- **Score 3:**
 - Hospitalized & **requiring low flow supplemental oxygen, defined as**

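### SAP hospitalisation rules 3 to 5 have no readmission exception, so a baseline-4 participant readmitted on low-flow oxygen at Day 28 scores 1 (improver) where the protocol scale gives 3 (not an improver)

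*SAP*

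**What the plan says.** **Protocol 8.1.1.** The score is the participant's worst state on the day. Category 3 is described as "Hospitalized on the day of assessment (including readmittance), and supplemental oxygen is required by the participant".

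**SAP 5.2.1, hospitalisation status.** Five rules are applied in order and the first that fits decides.
- Rule 5 (ordinary discharge): the discharge day counts as hospitalised, then "After this day, the participant will be considered “Not hospitalized” until day 28 or trial discontinuation, whichever comes first". Attachment 3 repeats it: "After this day, the subject will be considered “Not hospitalized” until day 28/trial discontinuation".
- Rule 4 (discharged although not ready): "The participant will be considered non hospitalized from 2 days after the day of discharge onwards until day 28", or trial discontinuation.
- Rule 3 (in hospital although ready to leave): the status holds "unless the status changes back to “not ready for discharge".

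None of these rules names readmission, and none of the 12 worked cases in Attachment 3 contains one.

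**SAP scoring.** Categories are tested from worst to best: "Once a participant fulfils the criteria for a category, the category is assigned to the participant and the evaluation stops". In Attachment 3, score 3 opens with "Hospitalized & requiring low flow supplemental oxygen, defined as", while scores 4 and 5 carry no hospitalisation condition. In 5.2.1 the heading of category 3 says the participant is hospitalised but its bullets do not repeat this. The first bullet to use the status rules is category 2: "Hospitalized according to the status described below".

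**Endpoints.** SAP 5.3.1 defines the first key secondary endpoint as an improvement of two or more categories at Day 28, and the estimand in 5.3.2 calls it sustained improvement at Day 28. Both use the 5.2.1 scale. For the primary endpoint, SAP 5.2.1 requires no documented loss through Day 28 or trial discontinuation. Protocol 4.1 and 9.4.2 require improvement sustained until Day 28, or until discharge or discontinuation.

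**The concern.** The SAP says it is to be read together with the protocol (SAP 1), yet for a participant discharged and later readmitted the two can give different scores on the same day. A participant back in hospital and needing oxygen can be recorded as not hospitalised, the best category on the scale.

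The affected endpoint is tested straight after the primary endpoint and gates the mortality test (Protocol 9.4). The SAP does recognise readmission elsewhere: total length of hospitalisation (5.4.1) counts re-hospitalisation periods. The same participant can therefore accumulate hospital days on one endpoint and be not hospitalised on another.

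**Working it through.** **Inputs.** Baseline scores 4 and 5 (primary analysis set, SAP 2.2.3), plus 3 for the ITT repeat. Possible true states on readmission are 2, 3, 4 and 5. A participant is an improver if baseline minus Day 28 score is at least 2. Oxygen data are assumed to be available.

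**Mapping.** The protocol scale keeps the true state. Under Attachment 3, states 4 and 5 are kept because they do not depend on hospitalisation status. States 3 and 2 require the participant to be hospitalised; rules 4 and 5 say otherwise, so both fall to 1.

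| Baseline | Readmitted at | Protocol change | Attachment 3 score | Attachment 3 change | Improver: protocol / Attachment 3 |
|---|---|---|---|---|---|
| 4 | 2 | 2 | 1 | 3 | yes / yes |
| 4 | 3 | 1 | 1 | 3 | **no / yes** |
| 4 | 4 | 0 | 4 | 0 | no / no |
| 4 | 5 | -1 | 5 | -1 | no / no |
| 5 | 2 | 3 | 1 | 4 | yes / yes |
| 5 | 3 | 2 | 1 | 4 | yes / yes |
| 5 | 4 | 1 | 4 | 1 | no / no |
| 5 | 5 | 0 | 5 | 0 | no / no |
| 3 | 2 | 1 | 1 | 2 | **no / yes** |
| 3 | 3 | 0 | 1 | 2 | **no / yes** |
| 3 | 4 | -1 | 4 | -1 | no / no |
| 3 | 5 | -2 | 5 | -2 | no / no |

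The result changes in 1 of 8 combinations in the primary set and in 3 of 12 in the ITT repeat.

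**A coherence check.** By the documents' flow conversion, 8 L/min is 52% and 7 L/min is 48%. Under Attachment 3 the same readmitted participant scores 4 at 8 L/min and 1 at 7 L/min, skipping 3 and 2.

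**Other endpoints.** Time to end of oxygen supplementation (SAP 5.4.1) loses its event if a score of 3 or worse follows. Attachment 3 hides a return to 3 in 2 of the 8 primary-set combinations (baseline 4 or 5, readmitted at 3). For the key secondary endpoint, the readmission has to cover Day 28. If the participant has left hospital again by then, improvement is restored, and on the SAP's definition only the date of sustained improvement moves.

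**Size.** The plan's own figure reproduces first. With 30% against 55%, 37 and 74 participants and a 1-sided 5% level:
- pooled rate = (37 x 0.30 + 74 x 0.55)/111 = 0.467
- null SE = sqrt(0.467 x 0.533 x (1/37 + 1/74)) = 0.1004
- alternative SE = sqrt(0.30 x 0.70/37 + 0.55 x 0.45/74) = 0.0950
- power = Phi((0.25 - 1.645 x 0.1004)/0.0950) = Phi(0.89) = 81.4%, consistent with the stated minimum of 80%.

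Each reclassified participant moves a proportion by 100/37 = 2.7 points in control or 100/74 = 1.4 points in sirukumab.

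Illustration only, since the documents give no rate. Suppose a share r of all improvers is reclassified in both arms, that is 51.8r participants (11.1 + 40.7 expected improvers):

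| Assumed r | Participants | Rates | Power |
|---|---|---|---|
| 2% | 1.0 | 29.4% / 53.9% | 80.1% |
| 5% | 2.6 | 28.5% / 52.3% | 78.1% |
| 10% | 5.2 | 27.0% / 49.5% | 74.5% |

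If r is 10% in one arm only, the 25-point difference becomes 55 - 27 = 28.0 points (control only) or 49.5 - 30 = 19.5 points (sirukumab only). The sign depends on where the readmissions fall.

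**The case against.** **The SAP also contradicts itself.** A reader might infer this, because the 5.2.1 bullets for category 3 omit hospitalisation and, read literally, give 3 where Attachment 3 gives 1. The documents do not support it as a clear second conflict. The heading of category 3 says hospitalised, 5.2.1 presents the status rules as serving the scale as a whole, and category 1 includes participants on a low level of oxygen. The literal reading would send a participant discharged on home oxygen to 3. A coherent reading of 5.2.1 also gives 1. The wording should be made explicit, no more.

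**Every readmission is scored as recovery.** This might be inferred from the rules alone, or from the headings of categories 4 and 5 in 5.2.1, which also say hospitalised. But Attachment 3, the operational derivation, puts no such condition on scores 4 and 5, so readmission at those levels still shows.

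**The data may not exist.** This stands in part. Daily assessments are scheduled only to Day 28 or discharge (Protocol 4.1). After discharge the calls collect readmission history and self-reported oxygen need, not FiO2 or SpO2 (Protocol 1.3, footnote n). Carrying the discharge status forward is an understandable convention for unscheduled data. It does not explain overriding a documented readmission.

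**The protocol allows improvement to be judged to discharge.** This stands for the primary endpoint: that wording partly supports rule 5, so a reader should not conclude that the primary endpoint is plainly mis-derived. The key secondary definitions do not have it. SAP 5.3.2 deals with discontinuation, carrying an earlier success forward, but not with discharge.

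**CRS (As observed) covers it.** It uses actual hospitalisation status and has both a time-to-improvement and a Day 28 endpoint, so it is a partial check. It also assigns category 4 by device rather than FiO2, so a difference between the scales could not be attributed to readmission.

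**Conclusion.** The point holds as a conflict between the SAP's derivation and the protocol scale. In the primary analysis set it is confined to baseline 4 readmitted on low-flow oxygen; in the ITT repeat it extends to baseline 3 readmitted at 2 or 3. It is clearest for improvement at Day 28 and also reaches time to end of oxygen supplementation. For the primary endpoint, the documents must first agree whether improvement runs to Day 28 or to discharge.

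The classification rests on Attachment 3 as written and on oxygen data being available during the readmission. Size and direction are unknown. A reader might take the illustration to mean that power falls below 80% or that the comparison favours one arm. Neither follows. The rates are assumed, and r is a share of all improvers, whereas only those with baseline 4 who were discharged and are back on low-flow oxygen on Day 28 count. The SAP's planning times are to sustained improvement and may already be net of such losses. What the documents support is the step per participant: 2.7 points in control or 1.4 in sirukumab.

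**What to change.** Before database lock of the primary analysis:

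1. Add to rules 3, 4 and 5 in SAP 5.2.1, and to Attachment 3: *unless readmitted by Day 28, in which case the participant is hospitalised from readmission to the next discharge and takes the worst category documented for each day*.
2. Put the hospitalisation condition into the category 3 bullets of 5.2.1, so that they match Attachment 3.
3. Add a worked readmission case to Attachment 3.
4. State whether the same rule applies to the primary endpoint, and align Protocol 4.1 and 9.4.2 with the SAP definition of sustained improvement. Settle this before item 1 is programmed, because the scale is shared.
5. Add a sensitivity analysis, labelled worst case, in which a readmission spanning Day 28 without oxygen data counts as loss of improvement. It is only a bound: baseline 4 readmitted at 2, and baseline 5 readmitted at 2 or 3, remain improvers on the protocol scale.

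The cost is SAP wording in two places, one example and minor programming. Readmissions are already recorded at the calls, and the length-of-hospitalisation endpoint already needs the periods. The downside is slightly fewer improvement events. Where oxygen data were not recorded during a readmission, only the sensitivity analysis can address it.

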1.3. Schedule of Activities (SoA)

Safety laboratory testing (hematology, chemistry, and coagulation tests) will routinely be performed by local laboratories (refer to Section 10.2 Appendix 2: Clinical Laboratory Tests and Section 10.3 Appendix 3: Clinical and Laboratory Assessments Described per Day).

	Screening Phase ^a	Phase Day 1 to Day 28			Post Day 28 Follow-up Phone Calls	
Day	Screening	Baseline ^a Day 1	Day 2 to Day 28 ^b or day of discharge from hospital ^{aa} , or study discontinuation, whichever comes first	Day 28 Visit if discharged earlier (Phone Call) Day 28 ±3 days	Day 56, Day 84, Day 112 ±7 days	
Week	Week 1	Week 1 (Day 2) to Week 4			Week 4	Week 8, 12, 16
General Screening/Baseline assessments						
ICF ^c	X					
Inclusion/exclusion criteria	X	X ^d				
Demographics, medical history ^c	X					
Targeted physical exam ^b	X		Any clinically significant findings to be reported			
Treatment administration						
Randomization ⁱ		X				
Administration of study intervention ⁱ		X				
Concomitant medication						
Concomitant medication recording	X	X	Throughout the study	X ⁿ	X ⁿ	
Respiratory function related assessments						
Type of supplemental oxygen	X	X	Once per day			
Resting SpO ₂ , FiO ₂ (if any) ^j	X	X	Minimum 4 times per day			
Arterial pH, PaO ₂ , PaCO ₂ ^j			As available			
Level of consciousness (Glasgow coma scale score) ^k	X	X	Once per day while in the ICU			
Pulmonary X-ray (or CT imaging or lung ultrasound if X-ray not available)	X ^{g,bb}		As per SOC, report upon worsening and last available			

	Screening Phase ^a	Phase Day 1 to Day 28				Post Day 28 Follow-up Phone Calls	
Day	Screening	Baseline ^a Day 1	Day 2 to Day 28 ^b or day of discharge from hospital ^{aa} , or study discontinuation, whichever comes first		Day 28 Visit if discharged earlier (Phone Call) Day 28 ±3 days	Day 56, Day 84, Day 112 ±7 days	
Week	Week 1		Week 1 (Day 2) to Week 4			Week 4	Week 8, 12, 16
General safety related assessments							
Standard 12-lead ECG	X ^{g,bb}		one ECG is to be taken between Day 4 and Day 8				
Vital signs (body temperature, pulse, SBP/DBP, respiratory rate)	X	X	As per SOC, minimum 4 times per day while in the ICU, afterwards once per day				
Any AE	X	X	Throughout the study				X ⁿ
Record discharge from ICU, discharge from hospital			As applicable				
Safety laboratory assessments^{dd}							
Hematology ^l	X ^g	X	Day 3, Day 7, Day 14, Day 21, Day 28 ^{cc}				
Chemistry ^l general safety	X ^g	X	Day 3, Day 7, Day 14, Day 21, Day 28 ^{cc}				

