6. STUDY INTERVENTION AND CONCOMITANT THERAPY

6.1. Study Intervention(s) Administered

Study intervention administration must be captured in the source documents and the electronic case report form (eCRF).

Sirukumab will be manufactured and provided under the responsibility of the sponsor. Refer to the IB for a list of excipients.²⁹

Participants need to receive study intervention preferably within 4 hours but no later than 6 hours after randomization.

Description of Interventions

The study intervention will be administered to the participant via an IV infusion using a 5% dextrose^a IV bag with a total volume of 50 mL.

Sirukumab will be injected into the bag for use in the treatment arm, the volume of the bag will be adjusted so that the total bag volume remains 50 mL.

No substance will be injected in the bag for the placebo arm, and a 5% dextrose^a 50 mL IV bag will be used as such.^b

An unblinded pharmacist or qualified staff member will prepare the IV bags before distribution to the clinic.

^a Dextrose is also commonly known and referred to as glucose.

^b Placebo will be provided locally by the study site.

Intervention Name	Sirukumab (CNTO136)
Type	Drug
Dose Formulation	Solution for infusion
Unit Dose Strength(s)	Sirukumab: 100 mg/mL
Dosage Level(s)	Sirukumab: 5 mg/kg single dose
Route of Administration	IV infusion
Use	Intervention
Investigational Medicinal Product (IMP)	Yes
Non-Investigational Medicinal Product/Auxiliary Medicinal Product (NIMP/AxMP)	No
Sourcing	Provided centrally by the sponsor
Packaging and Labeling (Labels will contain information to meet the applicable regulatory requirements.)	Each unit will be labeled with unique medication ID number.
	Not in child resistant packaging
Delivery Instructions	Refer to IPPI for instructions on IV infusion
Food/Fasting Requirement	Regardless of food intake

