2.2.3 Primary Analysis Set

The Primary analysis set consists of all participants in the ITT analysis set with confirmed critical COVID-19 disease defined as score of 4 or 5 on the CRS scale at baseline. For more details on CRS score please refer to Section 5: Efficacy. Treatment groups as randomized will be used for the analysis using this analysis set (Primary analysis set as Randomized).

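### A missing baseline CRS is filled from the 12 hours after randomisation, possibly post-dose, ahead of any earlier value

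*SAP*

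**What the plan says.** SAP 5.2.1 sets out three steps for the efficacy baseline.

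1. Default: "The 6-point ordinal CRS at the time of randomization request will be used as the baseline".
2. First fallback: "If the baseline assessment of the CRS is missing, the first available assessment within 12 hours after randomization will be used".
3. Second fallback: "If the latter is also missing, the last available assessment prior to baseline will be used".

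On dosing, Protocol 6.1 states: "Participants need to receive study intervention preferably within 4 hours but no later than 6 hours after randomization".

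The baseline score is then used twice in the primary analysis. SAP 5.2.1 defines the event relative to it: "Clinical Improvement is obtained if the score on the CRS improved with at least 2 categories with respect to the baseline score". SAP 2.2.3 selects the Primary analysis set by it, with critical disease "defined as score of 4 or 5 on the CRS scale at baseline".

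Three other places bear on the point. Footnote a of the Schedule of Activities and Protocol Section 8 ask sites to collect the data behind the CRS category before randomisation. SAP Attachment 3 ties the baseline CRS to data from the time of randomisation and mentions no later fallback. SAP 6.2, for viral load, puts pre-dose values first and allows a post-dose baseline only when no pre-dose value exists, and then only up to 60 minutes after the dose.

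**The concern.** A baseline should not be open to the influence of treatment. Here a value from after randomisation, and possibly from after the infusion, outranks one collected before randomisation. If the substitute is post-dose, it is in part an early outcome. Using it to fix the response threshold or to select the analysis set weakens the protection that randomisation gives. Blinding does not restore that protection, because the route is any effect of the drug on respiratory status, not knowledge of the allocation.

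The primary endpoint and the first key secondary endpoint (improvement at Day 28) depend on both the threshold and the set. Day 28 mortality depends on baseline CRS only through membership of the set.

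**Working it through.** **Step 1: the plan's own figures.** SAP 1.4 gives 111 participants (74 and 37) for at least 80% power with a two-sided 5% log-rank test. I simulated 6,000 trials with lognormal times in survivors (medians 16.8 and 28 days, SD of the log 0.9), mortality of 20% and 40%, and deaths and non-improvers censored at Day 28. Power was 81.3%, or 81.8% with times rounded up to whole days. For the key secondary endpoints at one-sided 5%, the normal approximation gives 81.4% for 30% against 55%, and 88.7% for 40% against 15%. All stated figures reproduce. None of them depends on how a missing baseline is filled.

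**Step 2: the time line.** The fallback window closes 12 hours after randomisation. Dosing is due by 6 hours at the latest, so the window stays open for at least 12 − 6 = 6 hours after the latest permitted dose, and for at least 12 − 4 = 8 hours if the preferred limit is met.

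**Step 3: how often the substitute would be post-dose.** The rule takes the first assessment after randomisation. Suppose assessments come every *g* hours at a random phase and dosing is *d* hours after randomisation. Then the share of substitutes that are post-dose is max(0, 1 − *d*/*g*). The Schedule of Activities asks for resting SpO2 and FiO2 "Minimum 4 times per day". Even spacing is my assumption and gives *g* = 24/4 = 6.

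| Dosing after randomisation | Share post-dose, *g* = 6 h |
|---|---|
| 1 h | 1 − 1/6 = 83% |
| 2 h | 1 − 2/6 = 67% |
| 3 h | 1 − 3/6 = 50% |
| 4 h | 1 − 4/6 = 33% |
| 6 h | 0% |

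For gaps of 4 to 12 hours and dosing at 0.5 to 6 hours, the range is 0% to 96%. A post-dose substitute is plainly possible. The documents do not show whether it would be the usual case.

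**Step 4: what a changed baseline does.**

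| Before randomisation | Substituted value | Effect |
|---|---|---|
| 4 | 5 | Target eases from CRS 2 or better to CRS 3 or better |
| 5 | 4 | Target tightens from CRS 3 or better to CRS 2 or better |
| 4 | 3 | Participant leaves the Primary analysis set |
| 3 | 4 | Participant enters it (only those enrolled before Amendment 5) |

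**Step 5: scale.** One affected participant is 1/37 = 2.7 percentage points of the control improvement rate or 1/74 = 1.4 points of the sirukumab rate. This is the weight of one person, not an estimate of bias. If 1%, 2%, 5% or 10% of baselines were missing (assumed rates), about 1, 2, 6 or 11 of 111 participants would be affected.

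As a deliberately one-sided illustration (4,000 simulated trials each), suppose only sirukumab participants were affected, and always to their disadvantage. Losing the event in 2%, 5% or 10% of them would lower power from 81% to about 78%, 73% or 61%. Dropping the earliest-responding 2%, 5% or 10% of that arm from the set would lower it to about 77%, 70% or 58%. Real substitutions would be mixed in direction and spread over both arms, so these figures are bounds under the stated assumptions, not forecasts.

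**The case against.** The strongest reply is that the rule will hardly ever be used. Sites are asked for the CRS data before randomisation, Amendment 5 requires category 4 or 5 for entry, and ventilation status is needed to stratify. This stands, and it limits the size of the problem. It also means that an earlier value will nearly always exist, so little is gained by ranking a later one ahead of it.

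A second reply is that closeness to randomisation is worth something in fast-changing disease. Screening can run over two calendar days, so the last earlier value may be stale. The SAP does not give this reason, but it is fair. It supports using a post-randomisation value that is still pre-dose, not one taken after the infusion.

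Third, nothing in the documents shows that one dose moves the CRS within hours. The Protocol 2.1.1 background reports reduced oxygen need within days for a related drug, in an uncontrolled series. The scale also records the worst state of the day. If the substitute is scored that way, a same-day fall from 4 to 3 would not register, although a worsening would. The SAP does not say whether daily scoring applies to the substitute.

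Three stronger readings are tempting and are not supported:

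- *The substitute is usually post-dose.* Step 3 shows that this depends on dosing time, which the documents do not report.
- *SAP 5.2.1 contradicts the pre-dose rule in SAP 2.5.* SAP 2.5 refers efficacy baselines to Section 5, and it allows post-dose baselines for viral load, height and weight. The contrast is one of standard: those exceptions apply only when no pre-dose value exists.
- *The ventilation stratum shifts with the substituted CRS.* SAP 4.2 takes baseline ventilation from the eCRF, or from the IWRS if the eCRF lacks it. The footnote to Table 2 in SAP 2.6 only says that CRS 5 corresponds to ventilation at randomisation.

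**Conclusion.** The fallback order is the wrong way round. A post-dose CRS can become the baseline that sets the improvement threshold and decides entry to the Primary analysis set, even when a pre-randomisation value is on file. This follows directly from SAP 5.2.1 read with Protocol 6.1 and needs no assumption.

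The size cannot be computed, because the documents give neither a rate of missing baselines nor actual dosing times. The rule should apply rarely, and no stated sample size, power or alpha is wrong. A reader might infer that the primary analysis is materially biased, or that a post-dose value must never be used. Neither follows. The first lacks any figure to support it. The second would leave a participant with no earlier value without a baseline, and so outside the Primary analysis set. The point is a cheap safeguard that should be put in place, not a flaw that undermines the design.

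**What to change.** Rewrite the fallback in SAP 5.2.1 so that a missing baseline CRS is filled in this order:

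1. the last available CRS before randomisation;
2. if there is none, the first value after randomisation that is timed before the start of infusion;
3. only if no pre-dose value exists, the first post-dose value within 12 hours of randomisation, flagged in the dataset.

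State whether a substituted value is a single assessment or a worst-of-day score. Align Attachment 3 with the new text. Report the number of substituted baselines by arm and by step. If any come from step 3, repeat the primary analysis without those participants as a sensitivity check.

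The cost is a short SAP edit before the primary database lock, with no new data and no effect on sample size. The downside is that a step 1 value may be up to about a day old.
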